- c. Subjects with clinical evidence of infection will have their CD4 (T helper cells), CD8 (cytotoxic T cells), and CD19 (B cells) absolute counts measured. Blood and other biological samples will also be collected for investigations of infective pathogens (eg, serological tests, quantitative polymerase chain reaction, microscopy, and culture) where appropriate. In subjects with infection, if any of their absolute cell counts meets the discontinuation thresholds, study drug will be discontinued. All subjects with severe infections will be discontinued from study drug. All subjects with herpes zoster (shingles) or ocular herpes infections will be discontinued from study drug, regardless of severity of presentation. Subjects with mild or moderate infection may continue treatment with study drug unless otherwise clinically indicated or otherwise specified below. Specifically, when any of the CD4 (T helper cells), CD8 (cytotoxic T cells), and CD19 (B cells) absolute counts are between the population-adjusted LLN and the discontinuation thresholds or have shown >33% reduction from baseline, subjects with infections of moderate intensity will be discontinued from study drug (eg, subjects whose infections are not localized, or subjects who are systemically unwell, or who require systemic anti-infective drug treatment). All subjects with infection who are discontinued from study drug will be followed for a period of 12 weeks or until the infection resolves/stabilizes or until the CD4 (T helper cells), CD8 (cytotoxic T cells), and CD19 (B cells) absolute counts have returned to greater than population-adjusted LLN (whichever comes latest). (revised per Amendment 02)

Table 2 Study Drug Actions for Lymphocyte Subset Absolute Counts and Infection

| Criterion | Severity of Infection | | | |
|--|---|---|---|------------------------|
| | None | Mild | Moderate | Severe |
| CD4 (T helper cells), CD8 (cytotoxic T cells), or CD19 (B cells) absolute counts below discontinuation threshold | If confirmed with repeat testing within 1 week, then discontinue study drug. | Discontinue study drug | Discontinue study drug | Discontinue study drug |

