| CD4 (T helper cells), CD8 (cytotoxic T cells), or CD19 (B cells) absolute counts between population-adjusted LLN and discontinuation threshold or >33% reduction from baseline in CD4 (T helper cells), CD8 (cytotoxic T cells), or CD19 (B cells) absolute counts | May continue treatment with study drug unless discontinuation is clinically indicated | May continue treatment with study drug unless discontinuation is clinically indicated | Discontinue study drug | Discontinue study drug |
| CD4 (T helper cells), CD8 (cytotoxic T cells), or CD19 (B cells) absolute counts always > population-adjusted LLN and no reduction from baseline >33% | May continue treatment with study drug unless discontinuation is clinically indicated | May continue treatment with study drug unless discontinuation is clinically indicated | May continue treatment with study drug unless discontinuation is clinically indicated (See (e) for exception) | Discontinue study drug |

LLN = lower limit of normal. Table revised per Amendment 02

- d. A subject with any skin rash of moderate to severe intensity, or any rash lasting more than 72 hours regardless of severity (see (e) for exception), will be discontinued from study drug and a dermatological consult will be requested regardless of whether the rash is considered drug-related or due to other causes. For cases where the investigator suspects a drug rash, regardless of severity, the subject will be discontinued from study drug, a dermatological consult will be requested, and a skin biopsy will be performed to confirm the diagnosis. The skin rash will be treated as per standard care and will be followed up until resolution regardless of etiology or severity.
- e. Subjects who develop moderate to severe oral or genital herpes should be discontinued from study drug. Subjects who develop a mild case of oral or genital herpes may remain on study drug even if the event lasts more than 72 hours.

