9.2.6 Clinical Risks and Mitigation Strategy

A number of safety aspects have been built into the design of this study in light of the preclinical and clinical safety data with E2609, and to mitigate clinical risk in the progression from 14 days of dosing in the MAD study to 18 months of treatment in this Phase 2 study. These safety aspects include the following:

- Two-stage study design: there will be a pause in recruitment after 60 subjects have been randomized to study drug (Stage A). Only after the safety of E2609 in these first 60 subjects (consisting of up to 12 weeks data for the later subjects and longer dosing periods for the earlier subjects) has been reviewed by the DSMB and considered acceptable, will randomization of further subjects into the study commence (Stage B). (revised per Amendment 01)
- Immunology-related and infection-related exclusion criteria

- Review of unblinded safety data by an independent DSMB at regular intervals
- Safety criteria for discontinuation of study drug based on CD4 (T helper cells), CD8 (cytotoxic T cells), CD19 (B cell) and other lymphocytes (absolute counts and percentage change from baseline), skin rash, reoccurrence of herpes virus infections including any oral herpes, genital herpes or shingles, other infections, MRI changes, ECGs, and pregnancy.

In addition to the features above, other safety aspects of this study designed to mitigate clinical risk include the following:

- Blinded safety data will be monitored by Eisai at regular intervals during the course of the study
- Routine safety assessments will include the monitoring and recording of all AEs and SAEs, monitoring of hematology, blood chemistry, and urinalysis, measurement of vital signs, regular ECGs, physical and neurological examinations, and centralized dermatological assessments (via photography) at regular intervals. AEs that might indicate signals of possible drug abuse potential will require a detailed follow-up. Subjects reporting AEs relating to abnormal dreams, nightmares, or sleep terror will be questioned on the frequency and impact of these events. To assess potential immunomodulatory effects, peripheral blood mononuclear cells (PBMCs) will be collected at baseline, during treatment, and posttreatment.

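### Section 9.3.3(c) stops study drug for all shingles and ocular herpes, but Table 2 in the same section allows continuation in three of its six mild or moderate cells

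*Protocol*

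**What the plan says.** The safety criteria for stopping study drug are in Protocol Section 9.3.3; Section 9.1.2.1 names that section as the place where they are detailed.

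- **Item (c), shingles and ocular herpes:** "All subjects with herpes zoster (shingles) or ocular herpes infections will be discontinued from study drug, regardless of severity of presentation".
- **Item (c), next sentence:** "Subjects with mild or moderate infection may continue treatment with study drug unless otherwise clinically indicated or otherwise specified below".
- **Item (c), infection with low counts:** "In subjects with infection, if any of their absolute cell counts meets the discontinuation thresholds, study drug will be discontinued".
- **Table 2** crosses three count strata with four severity columns (none, mild, moderate, severe). Row 1 is counts below the discontinuation threshold. Row 2 is counts between that threshold and the population-adjusted lower limit of normal (LLN), or a fall of more than 33% from baseline. Row 3 is counts always above the LLN with no such fall. For mild infection in rows 2 and 3 it says: "May continue treatment with study drug unless discontinuation is clinically indicated". The moderate cell of row 3 uses the same words and adds a pointer to (e).
- **Item (e), oral or genital herpes:** "Subjects who develop moderate to severe oral or genital herpes should be discontinued from study drug". It continues: "Subjects who develop a mild case of oral or genital herpes may remain on study drug even if the event lasts more than 72 hours".
- **Section 9.2.6** lists what the stopping criteria are based on, including "reoccurrence of herpes virus infections including any oral herpes, genital herpes or shingles".

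Section 9.3.3 appears twice in the protocol file, and both copies read the same on these points.

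**The concern.** A stopping rule should give one answer for one subject. Here the text of (c) and the table placed directly beneath it give different answers for some subjects with shingles or ocular herpes, and the protocol does not say which prevails within 9.3.3. Two drafting features make the table hard to read as simply yielding to the text. It carries an exception note, but only to (e), so a reader may conclude that no other herpes exception applies. And the general sentence in (c) excepts only what is specified after it, whereas the shingles and ocular herpes rule stands before it.

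The protocol itself treats these infections as important. Section 9.4.4 reports 4 subjects with symptomatic orolabial HSV1 relapse at 200 and 400 mg in Study 002. Section 9.3.2 excludes subjects with a history of ophthalmic shingles or ocular HSV infection. Section 9.5.1.5.2 makes ocular herpes serious in every case. Stage B runs at about 125 sites. Sites that read different passages could handle like subjects differently, and the by-group table of adverse events leading to discontinuation (Section 9.7.1.8.2) would then partly reflect which passage a site followed.

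**Working it through.** The plan gives no figure to reproduce and no formula applies. The check sets the instructions side by side for each herpes type, severity and count stratum.

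| Case | Table 2 row | Text of 9.3.3 | Table 2 | Result |
|---|---|---|---|---|
| Shingles or ocular herpes, mild | 2 | (c): stop | may continue | conflict |
| Shingles or ocular herpes, mild | 3 | (c): stop | may continue | conflict |
| Shingles or ocular herpes, moderate | 3 | (c): stop | may continue; pointer to (e) only | conflict |
| Shingles or ocular herpes, moderate | 2 | (c): stop | stop | agree |
| Shingles or ocular herpes, mild or moderate | 1 | (c): stop | stop | agree |
| Oral or genital herpes, mild | 1 | (e): may remain; (c): stop | stop | conflict on the wording |
| Oral or genital herpes, mild | 2, 3 | (e): may remain | may continue | agree |
| Oral or genital herpes, moderate | 1, 2, 3 | (e): stop | rows 1 and 2 stop; row 3 refers to (e) | agree |
| Any herpes, severe | 1, 2, 3 | stop | stop | agree |

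**Count of cells.** Three rows times two columns (mild, moderate) gives 3 × 2 = 6 cells. For shingles or ocular herpes, three conflict with (c): mild in rows 2 and 3, and moderate in row 3. The other three (mild and moderate in row 1, moderate in row 2) agree with it.

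**What item (d) closes.** Item (d) stops drug for a skin rash that is moderate to severe, or that lasts more than 72 hours at any severity; its cross-reference for an exception is to (e). Shingles presenting as such a rash is therefore stopped under (d), whatever Table 2 says. Two cases remain: mild shingles within the first 72 hours, and ocular herpes, which (d) does not address because it concerns skin rash.

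**Oral and genital herpes with low counts.** Item (e) sets no condition on counts. Item (c) and the mild cell of Table 2 row 1 stop drug when any infection coincides with counts below the threshold, and that cell has no pointer to (e). A subject with mild oral herpes and such counts may remain under (e) and is stopped under the other two.

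**Section 9.2.6 against 9.3.3.** The summary sets no severity limit on oral or genital herpes, while (e) does. It also names lymphocytes other than CD4, CD8 and CD19 as a basis for stopping, while items (a) to (c) set rules for those three subsets only.

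**The case against.** The strongest reply is that Table 2 permits and does not order. Item (c) is specific and mandatory, the table is generic to infection, and a site that stops a subject with shingles breaches neither passage. A careful reader may let the specific sentence govern. Other provisions also make unnoticed continuation less likely: rule (d) on rash, the detailed information on herpes zoster that must go to the Medical Monitor (Section 9.5.1.5.1), and the mandatory serious classification of ocular herpes, with reporting within 24 hours (Section 9.5.4.1). All of this stands and narrows the problem. It does not remove it, because a site that continues such a subject can point to a cell that allows it.

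A reader might also infer more than the documents support:

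- **That every mild oral or genital herpes event carries two opposite instructions, from 9.2.6 and from (e).** Section 9.2.6 is a risk overview that lists topics such as MRI changes and ECGs without thresholds, and Section 9.1.2.1 refers to 9.3.3 for the detail. The mismatch is one of summary wording.
- **That the safety board judges a dose by its rate of herpes discontinuation.** The protocol says only that the board reviews all safety data.
- **That herpes is an established signal at the doses used here.** Section 9.4.4 reports no infections at 100 mg or lower in Study 002, and says that exposure at this study's top dose is below that of the 100 mg dose.
- **That Table 2 is the passage sites work from.** The protocol does not say so.

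**Conclusion.** The point holds as an inconsistency inside the operative section. For shingles and ocular herpes, three of the six mild or moderate cells of Table 2 allow what (c) rules out; once (d) is applied, the gap is early mild shingles and mild or moderate ocular herpes in those cells. For mild oral or genital herpes with counts below the discontinuation threshold, (e) differs from both (c) and Table 2 row 1. The mismatch with 9.2.6 is secondary.

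The number of subjects affected cannot be stated, since the protocol gives no expected rate for these infections. The conclusion assumes that the passages are read as written and that no precedence is implied within 9.3.3. It makes no claim about the primary endpoint or any error rate. It matters because it bears on which subjects stay on drug. No view is taken on which clinical rule is right.

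**What to change.** The sponsor should reconcile Section 9.3.3(c), Table 2 and 9.3.3(e) so that each herpes type, severity and count stratum has one instruction, or state which passage takes precedence where they differ. The Table 2 exception notes and the sentence in (c) that refers only to later text should then be made to match. The Section 9.2.6 summary, both on herpes and on the lymphocyte subsets, should be aligned with the result, and both copies of 9.3.3 should carry the same text. The content of the rule is for the sponsor and the safety board. The cost is a wording change and a notice to sites; no visit, test or analysis is added.

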9.4 Treatments

9.4.1 Treatments Administered

For this study the test drug is E2609 and the control drug is placebo. All study drugs are to be administered orally, QD, with food.

Treatments to be administered in Stage A and Stage B are shown below and in [Figure 1](#).

The 2 highest E2609 doses (15 and 50 mg) taken into Stage B, after the PK/PD and safety review from Stage A, will be used for the mild to moderate AD population in Stage B. (revised per Amendment 01)

- Stage A: 3 doses (5, 15, and 50 mg) of E2609 or placebo
- Stage B, MCI/Prodromal Cohort: 3 doses (5, 15, and 50 mg) of E2609 or placebo
- Stage B, Mild to Moderate AD Cohort: 2 doses (15 and 50 mg) of E2609 or placebo. (revised per Amendment 01)

Study treatment will begin on Day 1 (at the study site) following Randomization and will continue for approximately 78 weeks. Please refer to [Table 7](#) and [Section 9.5.1.4.1](#) for specific information on drug administration on days when PK sampling is to be performed.

Study drug doses will remain the same for each individual subject unless the interim PK/PD analysis determines that an entire dose level requires adjustment ([Section 9.4.4](#)). See [Section 9.3.3](#) for safety-related discontinuation criteria of study drug. If a subject develops a concurrent illness during the treatment period, the investigator should discuss with the medical monitor on whether dosing with study drug needs to be temporarily suspended. As a general clinical guideline, dosing with study drug may be resumed after resolution or stabilization of the concurrent illness, after discussion with the medical monitor.

9.4.2 Identity of Investigational Product

E2609 tablets of 5-, 10-, and 25-mg dose strengths will be supplied. Placebo tablets of identical appearance will also be available. Each subject will receive 2 tablets, which combined will make up the required doses of E2609 5, 15, 50 mg, or placebo. The tablets

will be supplied by the Sponsor in labeled blister packs. The product release certificates for E2609 and placebo will be included in the clinical study report for this protocol.

Subjects will be stratified and randomized, and drug will be dispensed, via an interactive voice and web response system (IxRS) system (see [Section 9.4.3](#)).

The sponsor will provide the study drugs packaged in a double-blind configuration. Each subject's study tablets will consist of either E2609 or placebo, or both (see Section 9.4.2.3 for labeling details).

9.4.2.1 Chemical Name and Formula of E2609

- Test drug code: E2609
- Generic name: not applicable
- Chemical name: International Union of Pure and Applied Chemistry
- *N*-{3-[(4*aS*,5*R*,7*aS*)-2-Amino-5-methyl-4*a*,5-dihydro-4*H*furo[3,4-*d*][1,3]thiazin-7*a*(7*H*)-yl]-4-fluorophenyl}-5-(difluoromethyl)pyrazine-2-carboxamide
- Molecular formula: C₁₉H₁₈F₃N₅O₂S
- Relative molecular mass: 437.44

9.4.2.2 Comparator Drug

Not applicable.

9.4.2.3 Labeling for Study Drug

E2609 will be labeled in accordance with text that is in full regulatory compliance with each participating country and is translated into the required language(s) for each of those countries. The following information may be included but is not limited to:

- Protocol number
- For clinical study use only
- Name and address of the sponsor
- Chemical name/drug identifier (ID)
- Lot number/batch number
- Storage conditions, expiration date if necessary

9.4.2.4 Storage Conditions

Study drug will be stored in accordance with the labeled storage conditions. Temperature monitoring is required at the storage location to ensure that the study drug is maintained within an established temperature range. The investigator or designee (or if regionally required, the head of the medical institution) is responsible for ensuring that the temperature is monitored throughout the total duration of the study and that records are maintained; the temperature should be monitored continuously by using either an in-house validated data

acquisition system, a mechanical recording device, such as a calibrated chart recorder, or by manual means, such that minimum and maximum thermometric values over a specific time period can be recorded and retrieved as required.

9.4.3 Method of Assigning Subjects to Treatment Groups

Subjects will be assigned to treatments based on a computer-generated randomization scheme. The randomization scheme and identification for each subject will be included in the final clinical study report for this study. The doses and number of treatment groups to be used for Stage A (all subjects), for Stage B MCI/Prodromal subjects and Stage B for mild to moderate AD subjects are described in [Section 9.4.1](#). (revised per Amendment 01)

Randomization will be performed centrally by an IxRS. The IxRS or clinical supply vendor will generate the randomized blister card identification numbers. At enrollment, the investigator or designee will call the IxRS to register the subject information. At randomization (Visit 3), the IxRS will assign each subject a unique randomization number.

9.4.4 Selection of Doses in the Study

It is not known how the level of CSF or brain A β reduction is related to clinical efficacy. Therefore, in this study, doses will be selected such that at steady state, they will result in 25%, 50%, and 75% reduction in CSF A β levels from baseline to cover a broad range of PD effects.

In Study 007, the relative bioavailability of a tablet formulation of E2609 in the fed and the fasted states compared with the capsule formulation in the fasted state (used in Studies 001 and 002) was investigated. It was found that when the tablet form of E2609 (50 mg) was administered with food, the exposure (ie, AUC) of the parent drug E2609 was higher, with lower maximum observed concentrations and reduced exposure to the metabolites, compared with either formulation in the fasted state.

Based on the PK/PD modeling using data from healthy volunteer Studies 001, 002, and 007, doses of 5, 15, and 50 mg QD administered as the tablet formulation with food in this study should achieve CSF A β reduction from baseline of approximately 25%, 50%, and 75% at steady state, respectively ([Table 3](#)).

Table 3 Predicted Steady State Plasma PK Parameters and CSF Amyloid β Reduction From Baseline

| E2609 Tablet Daily Dose (mg) With Food | E2609 Plasma $C_{max,ss}$ (ng/ml) | E2609 Plasma $C_{ss,av}$ (ng/ml) | E2609 Plasma $AUC_{(0-24h)ss}$ (ng.h/ml) | % Reduction CSF BACE1 Activity | % Reduction CSF $A\beta(1-x)$ |
|--|-----------------------------------|----------------------------------|--|--------------------------------|-------------------------------|
| 5 | 6.2 | 3.3 | 80.3 | 16.2 | 33 |
| 15 | 18.6 | 10 | 240.9 | 36.6 | 56 |
| 50 | 62.1 | 33.5 | 803.0 | 65.7 | 79 |

$A\beta(1-x)$ = amyloid beta monomer from amino acid 1 to x, $AUC_{(0-24h)ss}$ = area under the concentration x time curve at steady state from time zero to 24 hours, BACE1 = Beta-amyloid converting enzyme, CSF = cerebrospinal fluid, $C_{ss,av}$ = average steady-state concentration, $C_{max,ss}$ = maximum plasma concentration at steady state, PK = pharmacokinetics.

The PK/PD modeling described above, which was conducted using data obtained from healthy volunteers, has also been supported by modeling of data from subjects with an underlying AD pathology (Study 101). Furthermore, external data with another BACE1 inhibitor (MK-8931) showed a similar PD effect in AD patients as in healthy volunteers (Forman, et al., 2013). Therefore we are confident that the modeling of E2609 effects in healthy subjects will be applicable for both MCI/Prodromal and mild to moderate AD dementia patients. (revised per Amendment 01)

The exposure of the highest dose in this study (50 mg QD tablet administered with food) is less than that of the 100 mg QD dose (capsule administered fasted) in Study 002.

The 100 mg QD dose administered for 14 days in Study 002 was well tolerated with no clinically significant changes in laboratory parameters, vital signs, or ECG parameters. On Day 15, for the 100 mg QD cohort in Study 002, there was a reduction of CD4 lymphocyte counts compared with placebo (CD4 lymphocyte counts on E2609 decreased by 3.1% from baseline, whereas the placebo control showed an increase of 8.7%), but this decrease was less than that observed at doses of 200 mg (22.9% decrease) or 400 mg (17.3% decrease). No subjects had infections or drug rash while receiving E2609 100 mg QD or at lower doses in Study 002, whereas at 200 and 400 mg QD, 4 subjects had symptomatic orolabial HSV1 relapses and 2 subjects at the highest dose had drug rash. The highest dose for Study 202 of 50 mg QD (tablet administered with food) is therefore expected to have a similar or better safety profile compared with the 100 mg QD capsule (administered fasted) in Study 002. Specific exclusion criteria, blinded and unblinded safety monitoring procedures, and safety criteria for discontinuation from study drug are included in this study in order to mitigate any immunology-related risk with E2609, particularly in light of the progression from 14 days of dosing (Study 002) to 18 months of dosing in this study.

In Stage A, all subjects will be randomized to receive either placebo or E2609 at 5, 15, or 50 mg QD. In Stage B, subjects in the MCI/Prodromal cohort will continue to be randomized to receive either placebo or E2609 at 5, 15, or 50 mg QD. In Stage B, subjects in the Mild to Moderate AD cohort will be randomized to receive either placebo or E2609 at 15 or 50 mg QD, but not the 5-mg QD dose. The rationale for not including an E2609 5-mg QD dose in the dose regimens for Stage B subjects with mild to moderate AD is that more

advanced disease may require greater reduction in CSF A β levels for comparable effects. (revised per Amendment 01)

Interim analyses of the E2609 PK and PD profiles will be performed on subjects who have provided CSF samples at Baseline and after 4 weeks of study drug. These data will be used to evaluate the CSF PD effects of E2609 doses, where PD is measured as reductions from baseline in CSF A β (1-x) levels. (revised per Amendments 01 and 02) The mean percentage change from baseline in CSF A β (1-x) measured after 4 weeks of treatment for each dose of E2609 and its 90% confidence interval will be derived. In addition, exploratory PK/PD modeling will be conducted. This PK/PD modeling will use the observed PK and PD data from Stage A and will relate the average steady state plasma concentration of E2609 to steady state CSF A β (1-x) percentage reduction from baseline after 4 weeks of dosing. (revised per Amendment 02)

If dose adjustment is required for Stage B, a protocol amendment reflecting the new doses will be submitted.

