9.5.1.4 Pharmacokinetic, Pharmacodynamic, Pharmacogenomic, and Other Biomarker Assessments

9.5.1.4.1 PHARMACOKINETIC ASSESSMENTS

Blood samples will be collected for the determination of the concentrations of E2609. For subjects who consent to CSF sample collection, CSF samples will be collected for the determination of E2609 concentrations. (revised per Amendment 02) Analyses of metabolite concentrations may be performed, depending on emerging data from other studies with E2609.

Samples from all subjects receiving active treatment will be analyzed. In addition, a predetermined percentage of placebo samples will be analyzed. Remaining placebo samples will be held in storage in the event that further confirmatory analysis is requested. Plasma concentrations of analytes will be quantified by liquid chromatography with tandem mass spectrometry methodology using a previously validated assay.

Blood samples will be collected as specified in Table 6 and Table 7. Two PK samples will be obtained: one at predose (trough) and another 1 to 6 hours postdose at Visits 5, 11, 14, and 16, and 4 to 8 hours postdose at Visit 7 and Visit 18 (or at the ED Visit). Therefore, subjects or their caregivers or informants must be instructed not to take their study drug at home on the day the PK sampling is performed. Instead, subjects will take the study drug with food at the clinic after collection of the predose PK sample. At Visit 7 and Visit 18 (or at the ED Visit) the PK blood sample should be collected shortly before or shortly after completing the LP. (revised per Amendment 01) Although the PK sampling procedures at the ED visit should follow those of Visit 18, in the event that study drug has already been discontinued prior to the ED visit, then no dosing will be conducted. However, a PK sample at trough (before LP) will be collected, followed by LP at approximately the same time as previous visits. A second PK blood sample will be collected as close as possible in time to the LP, either shortly before or shortly after the LP. (revised per Amendment 01)

Blood will also be drawn where possible at the first report of an SAE or severe unexpected AE and at its resolution.

See the laboratory manual (to be supplied to study sites) for a description of the collection, handling, and shipping procedures for PK samples.

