9.5.1.4.2 PHARMACODYNAMIC, PHARMACOGENOMIC, AND OTHER BIOMARKER, ASSESSMENTS

Biomarkers

Subjects who consent to CSF sample collection will be encouraged to stay at the site after completion of LP for medical observation (revised per Amendment 02). At Baseline, a CSF sample will be collected by LP (gravity drip method) after fasting (preferred), or at least 2 hours after the most recent meal. The timing of the Baseline LP needs to be scheduled carefully such that subsequent LPs (Visit 7 and Visit 18) can be performed between 4 and 8 hours postdose and at a similar time of day (± 1 hour) for each individual subject. At visits where cognitive tests are also performed, if the tests are to be performed on the same day, the LP must be performed after the cognitive tests have been completed and the subjects should rest and drink some fluid to hydrate before the LP. (revised per Amendment 01) The CSF sample will not be taken at the ED Visit if this visit occurs within 3 months of a previous CSF sample. The CSF sample will be used for PD assessments including but not limited to CSF $A\beta(1-x)$, $A\beta(1-42)$, t-tau, p-tau, and BACE. The plasma sample will be used for $A\beta(1-x)$ analysis and may be used for exploratory biomarker analyses (eg, miRNA). $A\beta(1-x)$ in both CSF and plasma will be measured using a commercially based enzyme-linked immunosorbent assay (ELISA). The pre- and post-screening analysis of CSF $A\beta(1-42)$, t-tau, and p tau will be performed using ELISAs. BACE1 levels will be measured using internally developed fluorescence resonance energy transfer and ELISA based assay(s). Substrates of BACE1 inhibition may also be explored using Western blots or other amenable methodology if clinical observations warrant and if analytes can be reliably tested in samples collected.

The blood sample collected for PD analyses at Baseline should be collected on the same day shortly before or shortly after completing the LP at Baseline. The sample should be collected at fasting or at least 2 hours after the most recent meal. (revised per Amendment 01)

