- v: For subjects who consent to CSF sample collection: All visits at which CSF samples are scheduled to be taken also include blood PK and PD assessments and so the subject will be dosed at the clinic on these days. A CSF sample will be collected by LP between 4 and 8 hours postdose and at the same time of day as the subject's Baseline LP (± 1 hour). The CSF sample will be taken with the subject fasting (preferred) or at least 2 hours after the most recent meal. A gravity drip collection method must be used. If the LP and the cognitive tests are performed on the same day, the LP must be performed after the cognitive tests have been completed and the subject should rest and drink some fluid to hydrate before the LP. Subjects will be encouraged to stay at the site after completion of LP for medical observation. The CSF sample will not be taken at the ED Visit if this visit occurs within 3 months of a previous CSF sample. If at an ED Visit, the subject has already stopped study drug, then no dosing will take place, but the

CSF sample will still be collected unless it was already collected within the past 3 months. (revised per Amendments 01 and 02)

- w: Subjects reporting adverse events relating to abnormal dreams, nightmares, or sleep terror will be questioned on the frequency and impact of these events.
- x: The first dose of study drug will be given to the subject at the study site and the subject will be encouraged to stay at the site for an appropriate period of time as determined by the PI or Safety Physician for postdose medical observation. (revised per Amendment 02)

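### The Stage A check of the doses for Stage B states only each E2609 dose's own change from baseline in CSF Aβ(1-x) and gives the concurrent placebo arm no role in that estimate

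*Protocol*

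**What the plan says.** Section 9.4.4 sets the aim: "doses will be selected such that at steady state, they will result in 25%, 50%, and 75% reduction in CSF" Aβ. Table 3 gives model predictions of 33%, 56% and 79% for 5, 15 and 50 mg. The interim in Stage A then checks the doses in subjects with CSF at Baseline and Week 4, "where PD is measured as reductions from baseline in CSF" Aβ(1-x). The estimate is the mean percentage change "measured after 4 weeks of treatment for each dose of E2609 and its 90% confidence interval will be derived". An exploratory model is added: "This PK/PD modeling will use the observed PK and PD data from Stage A", relating plasma concentration to percentage reduction from baseline. Section 9.1 and the synopsis repeat this.

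The result can have consequences. Under section 9.1, Stage B starts only after the doses have been evaluated, and section 9.4.4 adds: "If dose adjustment is required for Stage B, a protocol amendment reflecting the new doses will be submitted".

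Stage A randomizes 60 subjects 1:1:1:1 to placebo or one of three doses, with a target of 15 per arm (synopsis, Number of Subjects). CSF sampling is voluntary (section 5.3). Placebo subjects who consent follow the same lumbar puncture schedule as those on E2609.

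**The concern.** The interim is meant to show what E2609 does to CSF Aβ(1-x). A within-arm change from baseline is the drug effect together with whatever else moved between the two samples. A randomized placebo arm sampled at the same visits measures that other part, yet the stated estimate does not use it.

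Section 9.4.4 shows the difference with the sponsor's own data, on another marker in another study. In Study 002, CD4 counts on 100 mg fell by 3.1% from baseline while placebo rose by 8.7%, and the text reads the drug effect against placebo. As a ratio that is 0.969/1.087 = 0.891, a fall of about 11% and not 3%. The CSF check that follows in the same section has no such comparison.

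At stake is whether the 5 mg reading in particular can be taken as a drug effect when the doses for Stage B are settled.

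**Working it through.** The Protocol gives no sample size, SD, decision margin or expected placebo change for this check, so there is no figure of its own to reproduce.

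**Inputs**
- True reduction r: 33%, 56% and 79% (Table 3, section 9.4.4).
- Common change d between the two samples, unrelated to drug: not in the documents. Assumed range -15% to +15%.
- Pairs per arm: at most about 60/4 = 15. Fewer are likely because CSF is voluntary, so 5, 8 and 15 are shown.

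**Effect on the reading.** Observed reduction = 1 - (1 - r)(1 + d). At r = 33%, d = -10%: 1 - 0.67 × 0.90 = 0.397. At d = +10%: 1 - 0.67 × 1.10 = 0.263.

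| Assumed d | 5 mg, true 33% | 15 mg, true 56% | 50 mg, true 79% |
|---|---|---|---|
| -15% | 43% | 63% | 82% |
| -10% | 40% | 60% | 81% |
| 0 | 33% | 56% | 79% |
| +10% | 26% | 52% | 77% |
| +15% | 23% | 49% | 76% |

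The displacement is (1 - r) × |d|. For a 10% change it is 6.7 points at 5 mg, 4.4 at 15 mg and 2.1 at 50 mg. The 5 mg figure is close to the 8 points between the 25% target and the 33% prediction.

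**Read the other way.** Drug-attributable reduction = 1 - (1 - observed)/(1 + d). An observed 25% corresponds to 1 - 0.75/0.90 = 16.7% at d = -10%, or 1 - 0.75/1.10 = 31.8% at d = +10%. An observed 75% corresponds to 72.2% or 77.3%.

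**Price of the correction.** With n pairs in each arm and equal SDs on the log scale, the 90% half-width is t(0.95, n-1) × SD/√n within an arm and t(0.95, 2n-2) × SD × √(2/n) for dose against placebo. The SD cancels in their ratio:
- n = 5: 1.860 × 1.414/2.132 = 1.23
- n = 8: 1.761 × 1.414/1.895 = 1.31
- n = 15: 1.701 × 1.414/1.761 = 1.37

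**The case against.** Much can be said for the plan. The targets are themselves reductions from baseline, so the statistic matches what it is checked against. No numeric rule ties a dose change to this mean. The targets are approximate and meant to span a broad range, and even at d = ±15% the three doses stay ordered and well separated. The size of d is assumed. Section 9.7.1.7.2 allows pharmacodynamic analyses to be detailed in a separate statistical analysis plan. All of this limits the weight of the point. It does not remove it: the Protocol fixes the estimate itself in three places, and matching a from-baseline target does not show that the drug produced the change.

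Some stronger readings are tempting, but the documents do not support them.
- A reader might infer that the two punctures are done under generally different conditions. They are not: both use gravity drip, clock time is matched within 1 hour for each subject, and the meal rule is the same. For the first puncture the rule reads "a CSF sample will be collected by LP (gravity drip method) after fasting (preferred), or at least 2 hours after the most recent meal"; for those on treatment it reads "The CSF sample will be taken with the subject fasting (preferred) or at least 2 hours after the most recent meal". What differs is that at Week 4 "subjects will take the study drug with food at the clinic after collection of the predose PK sample", 4 to 8 hours before the puncture. Nothing in the Protocol says this shifts CSF Aβ.
- A reader might infer that note v of Table 7 contradicts dosing with food. Its second option, at least 2 hours after a meal, is compatible with a fed dose 4 to 8 hours earlier.
- A reader might cite the effect of food on E2609 exposure in section 9.4.4. That is a drug effect, absent on placebo, and a placebo contrast would not remove it.
- A reader might infer that placebo CSF is never used. Exploratory objective 3 compares E2609 with placebo at 4 weeks, section 9.7.1.6.3 analyses it, and the exploratory model does not exclude placebo subjects.

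**Conclusion.** The point holds in a limited form. The stated Stage A estimate is an uncorrected within-arm change for the active doses only, and it leaves out a concurrent randomized control that has the same samples. A common change of 10% in either direction would move the 5 mg reading by about 7 points and the 50 mg reading by about 2. These sizes rest on an assumed common change, which the placebo arm would measure, and on the Table 3 predictions as the true effects. Because no placebo change and no decision rule are given, a wrong dose decision is not shown. This is a worthwhile low-cost improvement whose value lies mainly at 5 mg. It implies no view on which doses are right.

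**What to change.** In section 9.4.4, section 9.1 and the synopsis, state that the interim also reports the placebo arm's Week 4 change in CSF Aβ(1-x), and for each dose a placebo-corrected estimate with its 90% confidence interval, beside the within-arm change. One suitable form is the Week 4 to Baseline ratio on the dose divided by that on placebo, analysed on the log scale. The model details can stay in the statistical analysis plan.

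The cost is a few lines of text and no new samples. The drawback is precision: the corrected interval is about 23% to 37% wider for 5 to 15 pairs per arm. Since the within-arm figure is still reported, nothing now planned is lost.
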